First, the effect of each factor on drug survival will be tested with a univariate Cox model. Thus, the hazard-ratios calculated are called “raw”. They will be presented with their 95% confidence interval and their associated p-value. Then, all potential factors for which the p-value resulting from univariate analysis is strictly less than 10% will be included in a multivariate Cox model. Predictive factors and their interactions will be chosen using a backward (step-down) selection. Predictive factors chosen will be those which have a p-value < 5%. In the case of a significant interaction, all individual components of the interaction will be “forced” in the model, whether they are statistically significant or not. The adjusted hazards-ratios thus obtained will be presented with their 95% confidence interval and their associated p-value.

Missing data will be managed using a method based on missing data indicators^(50, 51). This method is not a method of imputation of missing data. A fixed value will be assigned to missing observations, and a dummy variable (1/0) will be added to the multivariate model in order to indicate if the value of this variable is missing or not. If more than 10% of the patients have missing baseline covariates, a complete case analysis will also be performed as a sensitivity analysis. Additional methods for handling missing data may also be used. Further details will be provided in the statistical analysis plan as appropriate.

Secondary analyses

The impact of behavioural strategies (catastrophisation and coping) on Tofacitinib drug survival will be evaluated in patients suffering from RA. A Cox proportional hazards model will be used with the 5 dimensions in the coping questionnaire and the catastrophisation score collected at the baseline visit included as independent variables.

In a second phase and in a similar manner, a Cox model will be used to estimate the impact of the adaptive strategies under treatment. Therefore, the last evaluation available before discontinuation of treatment (or the last visit if a patient does not permanently discontinue treatment) and the change between this latter evaluation and the baseline value will be taken into account in separate models.

The correlation between behavioural strategies and effectiveness will be studied with Pearson's or Spearman's coefficient according to the nature of variables compared.

Interim analysis

Interim descriptive analyses will be conducted annually.

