6.1.1.2.1 PCS – Pain Catastrophising Scale

The Pain Catastrophising Scale (PCS) is a 13 item questionnaire around thoughts and emotions experienced during pain, with each question on a 5 point scale (0 = 'Not at all' to 4 = 'All the time'). There are three subscales of PCS: Rumination (thinking deeply), exaggeration and helplessness. [Table 2](#) shows an overview of the items which belong to each domain.

Table 2 Overview of Domains for PCS ([5](#))

Domain	Items
Rumination	8, 9, 10, 11
Exaggeration	6, 7, 13
Helplessness	1, 2, 3, 4, 5, 12

Total scores and domain scores are derived by summing the scores of the individual items. The highest possible score of PCS is 52, and a total score of ≥ 20 indicates a clinically relevant level of catastrophisation. PCS will be considered both in terms of individual domain scores and total scores. PCS total score will be analysed as a continuous variable as well as a dichotomous variable (<20 vs ≥ 20).

For the handling of missing data when deriving PCS scores, see Section [7.4](#).

PCS is collected at all visits (Inclusion visit, V1, V2, V3, V4, V5, V6 and any additional visits in the case of discontinuation of Tofacitinib).

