6.1.1.2.2 CSQ – Coping Strategies Questionnaire

The Coping Strategies Questionnaire (CSQ) evaluates cognitive coping and, in its French version, is split into 5 domains: “Distraction”, “Catastrophising”, “Distancing from Pain”, “Ignoring Pain Sensations” and “Praying”. The CSQ consists of 21 items in total and for each item, subjects rate the frequency of their use of each coping strategy on a 4-point Likert-type scale. CSQ is collected on the CRF as the following: 1: Never, 2: Sometimes, 3: Often and 4: Very often. In order to consider values comparable to the standard CSQ French Version, the following mapping will be done.

CSQ Text Value	CRF Value	Map to standard value
Never	1	0
Sometimes	2	1
Often	3	2
Very Often	4	3

This endpoint is considered in terms of the 5 domains, and a total score is not considered for CSQ. Domain scores are derived by summing the individual items scores that make-up the domain. Details of the 5 domains are provided below.

Domain	Items as numbered on CRF	Domain Score Range
Distraction	2, 10, 11, 19, 20	0 – 15
Catastrophising	3, 9, 15, 18	0 -12
Distancing from Pain	1, 5, 13, 21	0 – 12
Ignoring Pain Sensations	6, 7, 8, 14, 16	0 – 15
Praying	4, 12, 17	0 - 9

CSQ is collected at all visits (Inclusion visit, V1, V2, V3, V4, V5, V6 and any additional visits in the case of discontinuation of Tofacitinib).

For the handling of missing CSQ data, see Section [7.5](#).

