8.1.1 Analysis of Time to Event Data

8.1.1.1 Cox Proportional Hazards

Cox proportional hazards (PH) models will be used to analyse time to event data, where the event of interest is duration of Tofacitinib drug survival described in Section **Error! Reference source not found.** If a patient is not recorded as having permanently discontinued Tofacitinib, which is the event of interest, then they will have their time of follow-up censored at the date of their last visit.

For the primary analysis, univariate Cox PH models will be created for all of the potential predictive factors, see [Figure 2](#) in Section [8.2.3](#), that is a separate Cox PH model will be created for each factor. If the variable significantly impacts Tofacitinib drug survival at the 10% level then the factor will be put forward into a multivariate model.

Once the univariate model selection is complete, backwards selection will be used to remove factors from the multivariate model which do not have a significant p value at the 5% level. The covariate with the highest p value will be removed in turn until all factors have a p value less than 0.05. If a significant interaction is found then the individual factors of this interaction will be kept in the model, regardless of their p value. A significant interaction is tested for between all variables in the multivariate model.

Furthermore, for the primary analysis a table showing all of the 95% confidence intervals and p values for the “raw” hazard ratios coming from the univariate models will be created. This will be for all of the factors in [Figure 2](#), regardless of whether they’re included in the multivariate model.

For the secondary analysis, a multivariate Cox PH model will be created including the scores from the 5 domains of the CSQ at baseline and the total PCS score at baseline included as covariates.

A further two Cox PH models will be produced for the secondary analysis, for CSQ and PCS: the first including the last evaluation available before discontinuation (or last visit if

patient does not discontinue during the study) and the second including change from baseline to the last recorded measurement.

The SAS procedure PROC PHREG will be used to fit any Cox PH models and check the assumption of proportional hazards. If the assumption of proportional hazards is violated then alternative models will be considered.

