8.1.3 Logistic Regression

Logistic regression will be used to analyse the relationship between binary endpoints and behavioural strategies. The binary endpoints will be the response variables at Months 3, 6, 12 and 24 and PSC total score and the 5 domains of the CSQ will be fitted as a continuous, independent variables in separate univariate models. Estimates for the odds ratio's (OR's), confidence intervals (CI's) and p-values will be presented.

Reference code for logistic regression:

```
ODS OUTPUT oddsratios = _out1 parameterestimates = _out2;
PROC LOGISTIC DATA = <data>;
  MODEL <binary endpoint at visit> = <behavioural endpoint at visit>;
  RUN;
  ODS OUTPUT CLOSE;
```

Where ODS OUTPUT option odds ratios selects the OR's and CI's, and parameter estimates can be used to select the p-value.

The association between baseline PCS total score (<20 vs ≥ 20) and baseline characteristics will also be explored using a logistic regression. A univariate analysis will first be performed with a significance level set at 10%. All significant characteristics will be put forward into a multivariate model. A backward selection will be used to remove

characteristics from the multivariate model which do not have a significant p value at the 5% level.

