8.2.6.1 Behavioural Strategies – PCS and CSQ

The impact of behavioural strategies (PCS total score and 5 domains of the CSQ) on Tofacitinib drug survival will be analysed, using three multivariate Cox PH models as described in Section 8.1.1.1 Cox Proportional Hazards.

PCS (individual domain scores and total scores) and CSQ (individual domain scores) will also be summarised as continuous variables as per Section **Error! Reference source not found.** PCS total score will also be summarised as a dichotomous variable (<20 vs ≥ 20) as per Section **Error! Reference source not found.**

Correlations between the behavioural strategies (PCS total score and 5 domains of the CSQ) and each of the endpoints listed below will be investigated as outlined in Section **Error! Reference source not found.**, for the endpoints seen in Figure 3:

- DAS28-4 ESR
- DAS28-4 CRP
- TJC
- SJC
- Duration of morning stiffness
- GIRERD Questionnaire
- EuroQoL EQ-5D-3L
- SF-12v2 Questionnaire
- FACIT-Fatigue Questionnaire
- DAS28 (EULAR Criteria)
- Pain

Figure 3 Timepoints for correlation analyses

Behavioural Strategies Timepoint	Effectiveness Endpoint Timepoint
M0 (Baseline)	M3
M0 (Baseline)	CFB to M3 (M3-M0)
M3	M3
M3	CFB to M3 (M3-M0)
CFB to M3 (M3-M0)	M3
CFB to M3 (M3-M0)	CFB to M3 (M3-M0)
M0 (Baseline)	M6
M0 (Baseline)	CFB to M6 (M6-M0)
M6	M6
M6	CFB to M6 (M6-M0)
CFB to M6 (M6-M0)	M6
CFB to M6 (M6-M0)	CFB to M6 (M6-M0)
M0 (Baseline)	M12
M0 (Baseline)	CFB to M12 (M12-M0)
M12	M12
M12	CFB to M12 (M12-M0)
CFB to M12 (M12-M0)	M12
CFB to M12 (M12-M0)	CFB to M12 (M12-M0)
M0 (Baseline)	M24
M0 (Baseline)	CFB to M24 (M24-M0)
M24	M24
M24	CFB to M24 (M24-M0)
CFB to M24 (M24-M0)	M24
CFB to M24 (M24-M0)	CFB to M24 (M24-M0)

M = Month. CFB = Change from baseline.

Logistic regression will be considered to assess the relationship between behavioural strategies (PCS total score and 5 domains of the CSQ) and each of the binary endpoints listed below as outlined in Section **Error! Reference source not found.**, with a separate model created for each of the timepoints seen in Figure 4:

- LDA
- Patients in remission
- FiRST Questionnaire

Figure 4 Timepoints for logistic regression

Behavioural Strategies Timepoint	Effectiveness Endpoint Timepoint
M0 (Baseline)	M3
M3	M3
CFB to M3 (M3–M0)	M3
M0 (Baseline)	M6
M6	M6
CFB to M6 (M6–M0)	M6
M0 (Baseline)	M12
M12	M12
CFB to M12 (M12–M0)	M12
M0 (Baseline)	M24
M24	M24
CFB to M24 (M24–M0)	M24

M = Month. CFB = Change from baseline.

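### The three behavioural Cox models enter PCS total alongside the CSQ Catastrophising domain with no joint test or separate fits, so both can be non-significant when the trait matters

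*SAP*

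**What the plan says.** SAP 8.2.6.1 states that the impact of PCS total and the five CSQ domains "on Tofacitinib drug survival will be analysed, using three multivariate Cox PH models". SAP 8.1.1.1 gives the content of the first: the "5 domains of the CSQ at baseline and the total PCS score at baseline included as covariates". Protocol 9.7 specifies the same model, "with the 5 dimensions in the coping questionnaire and the catastrophisation score collected at the baseline visit included as independent variables". The other two follow in SAP 8.1.1.1: "A further two Cox PH models will be produced for the secondary analysis, for CSQ and PCS", one using the last evaluation and one the change from baseline. SAP Table 8 lists all three with both instruments as covariates.

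On content, SAP 6.1.1.2.1 says that a PCS total of 20 or more "indicates a clinically relevant level of catastrophisation". SAP 6.1.1.2.2 says: "The Coping Strategies Questionnaire (CSQ) evaluates cognitive coping and, in its French version, is split into 5 domains". The second domain listed is Catastrophising (CRF items 3, 9, 15 and 18, range 0 to 12). Protocol 9.3.2.2 appears to call the same factor Dramatisation.

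Elsewhere the SAP treats overlapping scores differently. For binary endpoints (8.1.3), PCS total and the CSQ domains "will be fitted as a continuous, independent variables in separate univariate models". For SF-12 (8.2.3) it anticipates collinearity and foresees fitting the summary measures and the health domains in separate models. The behavioural Cox models have no such provision; the only diagnostic named for them is the proportional hazards check.

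**The concern.** In the joint model the PCS hazard ratio compares patients who differ on PCS but have the same CSQ Catastrophising score, and the reverse holds for the CSQ domain. If the two scores largely measure one trait, each coefficient carries only the part that the other does not explain, with a wider interval.

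The objective is the impact of behavioural strategies on drug survival, and the protocol summary labels this the key secondary analysis. These models report a p-value for each coefficient at the 5% level. Two non-significant catastrophising lines would be easy to read as showing that catastrophising does not matter, when the data may only be unable to say which of the two scores carries the effect.

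**Working it through.** **Inputs from the documents.** Protocol 9.5: 50 candidate factors, 30% passing the univariate screen, 10 events per variable, 50% drug survival at 24 months. SAP 8.1.1.1: two-sided alpha 0.05, no multiplicity adjustment. Six covariates in each behavioural model.

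**The plan's own figure.** Events = 10 × (50 × 0.30) = 150; N = 150 / 0.50 = 300. Both reproduce. In a six-covariate model this is 150 / 6 = 25 events per variable, so overfitting is not the issue.

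**Assumptions not in the documents.** Correlation ρ between PCS total and CSQ Catastrophising of 0.5 to 0.8; a marginal HR of 1.3 per SD on each scale; both scales carrying the shared trait equally; the other four CSQ domains unrelated to these two; all 150 events usable.

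**Formulas**, with b = ln(1.3) = 0.2624 and D = 150:

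- Scale entered without the other: power = Φ(b√D − 1.96) = Φ(3.213 − 1.96) = 0.895.
- Coefficient of each scale in the joint model: b/(1+ρ).
- Power per scale in the joint model: Φ([b/(1+ρ)]·√(D(1−ρ²)) − 1.96), plus a negligible opposite tail.
- 2-df test of the pair: noncentral chi-square with noncentrality 2Db²/(1+ρ).

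| ρ | variance inflation 1/(1−ρ²) | HR per scale in joint model | power per scale | noncentrality | power, 2-df test |
|---|---|---|---|---|---|
| 0.5 | 1.33 | 1.19 | 46% | 13.8 | 92% |
| 0.7 | 1.96 | 1.17 | 27% | 12.1 | 89% |
| 0.8 | 2.78 | 1.16 | 19% | 11.5 | 87% |

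**Simulation check** (1,500 Cox fits per setting, 300 patients, about 151 events, six covariates, HR 1.3; the 2-df test was a likelihood ratio test). For ρ = 0.5, 0.7 and 0.8, power for PCS without CSQ Catastrophising was 88%, 89% and 88%; for PCS in the joint model 43%, 30% and 16%; for the 2-df test 92%, 88% and 85%. At least one of the two scores was significant in 78%, 56% and 35% of runs, so both were non-significant in 22%, 44% and 65%.

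**Sensitivity to the assumptions.** With a marginal HR of 1.25, power alone is 78%, per scale in the joint model 35%, 21% and 15%, and for the 2-df test 81%, 76% and 73%. With 1.4, power per scale in the joint model is 66%, 41% and 28%, against more than 98% alone. If PCS kept an HR of 1.3 at fixed CSQ Catastrophising, only the standard error would grow (by 15%, 40% and 67%), and PCS power in the joint model would be 80%, 63% and 49%. That milder case does not describe two scores sharing one trait.

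**The case against.** Much can be said for the plan as written.

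- **The joint model is a legitimate reading of the objective.** The objective concerns behavioural strategies as a whole, catastrophising and coping together, and the six-covariate model is pre-specified in the protocol. A reader might infer that joint entry biases the estimates or that the model should be replaced. The documents do not support that: the conditional hazard ratios are valid answers to a conditional question. This stands, and the planned models should stay.
- **Separate baseline fits may already exist.** SAP 8.1.1.1 plans a univariate Cox model for every Figure 2 factor and tabulates all the raw hazard ratios. Figure 2 is not shown in the text available, so nobody can conclude from it that PCS and CSQ are never fitted separately against drug survival. If they are listed, the concern is partly met at baseline. SAP 8.2.3 says that all Figure 2 factors are baseline predictors, so the last-evaluation and change models would still have no separate fit.
- **No formal hypotheses.** SAP section 4 says so, and hazard ratios with 95% intervals will be shown, so collinearity would appear as wide intervals. This lowers the stakes, but p-values at 5% are still reported and the risk of misreading remains.
- **The overlap is inferred from a domain label.** No item text or PCS–CSQ correlation is given, and the protocol uses another label. The overlap is plausible, but its size is unknown.

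**Conclusion.** The point holds as a modest improvement to the secondary analysis. The documents establish that all three behavioural Cox models adjust PCS total for a CSQ domain named Catastrophising, and that this section plans no joint test, separate fit or collinearity check. It follows that a real effect of the trait can go unseen in the individual coefficients.

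The documents do not fix how large the loss is. Under the shared-trait assumptions above, power for each scale falls from 90% to between 46% and 19%, while the 2-df test stays between 92% and 87%. The absolute figures are likely to be optimistic: PCS and CSQ are not imputed and Table 8 applies no missing-data method, so patients lacking any of the six scores drop out and fewer than 150 events may be available.

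Two stronger readings do not follow: that the analysis will miss an effect of catastrophising, and that a PCS-only model should become the sole basis for the conclusion. The first needs a correlation that the documents do not give. The second would displace the protocol's pre-specified model, which estimates what it sets out to estimate.

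**What to change.** Keep the three planned models and add to SAP 8.1.1.1, 8.2.6.1 and Table 8:

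1. For each model, a 2-df Wald test of PCS total and CSQ Catastrophising together.
2. For each model, two supplementary fits: PCS total without the CSQ, and the five CSQ domains without PCS.
3. The correlation between PCS total and CSQ Catastrophising on each of the three scales (baseline, last evaluation, change).
4. A sentence fixed in advance: two non-significant individual coefficients in a joint model will not be read as no effect of catastrophising unless the 2-df test is also non-significant.

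The cost is SAP wording, 3 × 2 = 6 extra fits and three joint tests on data already collected. The downside is a few more p-values without multiplicity adjustment, so the added fits should be labelled supplementary. A side benefit is that a PCS-only model keeps patients whose CSQ is incomplete.

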6 ENDPOINTS AND COVARIATES

6.1 EFFICACY/EFFECTIVENESS ENDPOINT(S)

All study data will be collected by the participating physician directly in the eCRF.

Baseline measurements for all endpoints are the last measurement before Tofacitinib treatment, up to 28 days before starting Tofacitinib. Change from baseline at a timepoint will be calculated as:

Measurement at visit – Measurement at baseline

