6.1.1.2.15 SF-12v2 Questionnaire

The short form-12 version 2 (SF-12v2) health survey consists of 12 questions, which evaluate 8 aspects of quality of life (QoL). All items, domain scores and summary measures are scored so that a higher score indicates a better health state. The scores will

be derived based on the guidelines provided in User's Manual for the SF-12v2 Health Survey, Third Edition (4).

Table 6 shows an overview of the SF-12v2 questionnaire domains.

Table 6 Overview of Domains for SF-12v2 questionnaire

Domain	Item numbers
Physical Functioning (PF)	2a, 2b
Role-Physical (RP)	3a, 3b
Bodily Pain (BP)	5
General Health (GH)	1
Vitality (VT)	6b
Social Functioning (SF)	7
Role-Emotional (RE)	4a, 4b
Mental Health (MH)	6a, 6c

SF-12v12 will be considered in terms of the physical and mental component summary measures (PCS_{SF12} and MCS) as well as the 8 health domains seen in [Table 6](#).

The SF-12v2 Questionnaire is completed at all visits (Inclusion visit, V1, V2, V3, V4, V5, V6 and any additional visits in the case of discontinuation of Tofacitinib).

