6.1.1.2.16 FACIT-Fatigue Questionnaire

The Functional Assessment of Chronic Illness Therapy-Fatigue (FACIT-Fatigue) questionnaire consists of 13 self evaluated questions. The questions consider the patients functionality over the 7 days prior to completing the questionnaire. Each question has a response of values 0 to 4. The FACIT-Fatigue total score is derived by summing the response to each question which gives a value between 0 and 52. Higher scores represent better patient status (less fatigue).

For some of the questions, the scale indicates a higher score is better and for others a lower score is better. Therefore, in order to correct this and ensure that higher scores represent better patient status, the items marked with a ‘-’ in the

[Table 7](#) will be reversed by subtracting the response from ‘4’ before summing all subscale items.

Table 7 FACIT-Fatigue Item subscale

Item No.	Question	+/-
HI7	I feel fatigued	-
HI12	I feel weak all over	-
An1	I feel listless (“washed out”)	-
An2	I feel tired	-
An3	I have trouble starting things because I am tired	-

An4	I have trouble finishing things because I am tired	-
An5	I have energy	+
An7	I am able to do my usual activities	+
An8	I need to sleep during the day	-
An12	I am too tired to eat	-
An14	I need help doing my usual activities	-
An15	I am frustrated by being too tired to do the things I want to do	-
An16	I have to limit my social activity because I am tired	-

For handling of missing data, see Section 0.

The FACIT-Fatigue Questionnaire is completed at all visits (Inclusion visit, V1, V2, V3, V4, V5, V6 and any additional visits in the case of discontinuation of Tofacitinib).

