8.1.2 Correlation Analysis

The correlation between behavioural strategies (measured by PCS total score and 5 domains of the CSQ) and effectiveness will be studied with Pearson's or Spearman's coefficient according to the nature of variables compared. This will be calculated for all effectiveness endpoints. To investigate the relationship between a categorical variable and a continuous variable, boxplots for each category will be produced and a visual comparison will be made (there will be no correlation co-efficient for these comparisons).

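### Correlating baseline PCS and CSQ scores with change in effectiveness, without adjusting for baseline effectiveness, can show baseline severity as a behavioural effect

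*SAP*

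**What the plan says.** The protocol (section 8) lists the correlation between behavioural strategies and effectiveness as a secondary objective. SAP 8.2.6.1 implements it: "Correlations between the behavioural strategies (PCS total score and 5 domains of the CSQ) and each of the endpoints listed below will be investigated". SAP Figure 3 gives six pairings at each of M3, M6, M12 and M24, 24 in all. Twelve use change in effectiveness: four against baseline behaviour, four against behaviour at the same visit, and four against change in behaviour.

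SAP 6.1 defines change as "Measurement at visit – Measurement at baseline". Under SAP 8.1.2 the association "will be studied with Pearson's or Spearman's coefficient according to the nature of variables compared". Categorical endpoints get boxplots, and "there will be no correlation co-efficient for these comparisons". For low disease activity (LDA), remission and FiRST, SAP 8.1.3 says the behaviour scores "will be fitted as a continuous, independent variables in separate univariate models". SAP Figure 4 pairs baseline behaviour with the binary endpoint at the same four visits.

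Neither document names the baseline effectiveness value as a covariate for this objective. SAP 8.2.6.5 does plan to explore whether baseline PCS (below 20 versus 20 or more) is associated with baseline pain, joint counts, DAS28, FACIT-Fatigue, SF-12 and EQ-5D-3L.

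**The concern.** Because change is visit minus baseline, the baseline value enters with a minus sign. Suppose patients with high PCS also have worse disease at baseline, and that follow-up depends on behaviour only through baseline. Those patients start worse and regress further, so high PCS appears to go with more improvement.

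The univariate logistic models lean the other way. High-PCS patients start further from LDA or remission and reach it less often.

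The study could therefore report that catastrophisers improve more and also that they respond less often, with both results coming from baseline severity. A baseline association is plausible on the study's own rationale: the protocol (sections 4 and 7) says behavioural strategies can influence symptom intensity, and SAP 8.2.6.5 looks for such an association.

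**Working it through.** **Sample size.** The documents state no figure for the correlation analysis. Protocol 9.5 uses N = 10k/p. With k = 50 × 0.3 = 15 and p = 0.5, this gives 150 events and N = 150/0.5 = 300, as stated. SAP 8.2.6 restricts the correlations to on-treatment data, so at 50% drug survival about 300 × 0.5 = 150 patients remain at M24. SAP 2.1 still says 500 patients. A larger N leaves the expected coefficient unchanged and only makes it significant more often.

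**Assumed inputs (not in the documents).** ρ is the correlation of baseline behaviour with baseline effectiveness, r the correlation of baseline with visit effectiveness, and s the follow-up SD divided by the baseline SD. No effect means that baseline behaviour is unrelated to the visit value given the observed baseline value.

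**Formula for baseline behaviour versus change:**

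corr = ρ(rs − 1) / √(1 + s² − 2rs), which is −ρ√((1 − r)/2) when s = 1.

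For ρ = 0.3, r = 0.5, s = 1: 0.3 × (0.5 − 1)/√1 = −0.15.

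Expected coefficient with s = 1, for an endpoint where higher is worse. In brackets is the chance of p < 0.05 at N = 300, if a test is attached (Fisher z, two-sided 5%):

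| ρ | r = 0.3 | r = 0.5 | r = 0.7 |
|---|---|---|---|
| 0.2 | −0.12 (54%) | −0.10 (41%) | −0.08 (27%) |
| 0.3 | −0.18 (87%) | −0.15 (74%) | −0.12 (52%) |
| 0.4 | −0.24 (99%) | −0.20 (94%) | −0.15 (77%) |

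The critical |r| is 0.113 at N = 300 and 0.160 at N = 150.

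**Sensitivity to the assumptions.**
- ρ = 0 gives 0.
- ρ = −0.3, r = 0.5, s = 1 gives +0.15. This is the case for FACIT-Fatigue, SF-12 ("a higher score indicates a better health state") and EQ-5D-3L (best state scored 1), if the behaviour score goes with worse status.
- ρ = 0.3, r = 0.5, s = 1.25 gives 0.3 × (−0.375)/√1.3125 = −0.10.
- ρ = 0.3, r = 0.7, s = 1.5 gives 0.3 × 0.05/√1.15 = +0.01.

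**Simulation (4,000 runs; ρ = 0.3, r = 0.5, s = 1).** At N = 300 the planned coefficient averages −0.15 and is significant in 74% of runs; the partial correlation given baseline averages 0.00 and is significant in 4.8%. At N = 150 the rates are 47% and 5.2%.

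**Other rows in the same scenario.** Baseline behaviour versus the raw visit value gives ρ × r = +0.15. With a behaviour autocorrelation of 0.6 (assumed), same-visit behaviour versus change gives +0.12, and change versus change +0.30. Neither produced a significant negative result.

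**Logistic models (simulated; n = 250, r = 0.5, about 40% in LDA, no effect given baseline).** At ρ = 0.3 the univariate model is significant in about 44% of runs, against 4% with baseline severity added. At ρ = 0.4 the figures are 68% and about 5%. More improvement and less LDA are both significant in the same simulated study in 3%, 23% and 60% of runs for ρ = 0.2, 0.3 and 0.4.

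**The case against.** The strongest counter-argument is that change-score and baseline-adjusted analyses answer different questions, and adjustment is not always the safer one. Suppose behaviour relates to a stable true disease level, and each measurement is that level plus independent error. Change is then pure error and its correlation with behaviour is exactly 0. The partial correlation is ρ(1 − r)/√((1 − ρ²)(1 − r²)). For ρ = 0.4 and r = 0.5 this is 0.2/√(0.84 × 0.75) = +0.25, which is spurious. This stands, and it rules out replacing the planned coefficients.

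Three further points stand. The inputs are assumed, and because entry requires moderate-to-severe active disease, baseline spread may be restricted and equal SDs cannot be taken for granted. SAP 8.1.2 specifies coefficients without p-values, so the significance rates apply only if tests are added; p-values are planned for the logistic models. The analyses are secondary and SAP section 4 states no formal hypotheses, so an unadjusted association is a legitimate description.

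It is also true that Figure 3 shows raw visit values beside change. That does not resolve the matter, because those rows are unadjusted too and lean the other way.

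A reader might infer that all 12 change-in-effectiveness rows are driven negative. The formula covers only the four with baseline behaviour; in the scenario above the other eight are positive.

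**Conclusion.** The concern holds for the four rows of Figure 3 that set baseline behaviour against change in effectiveness. There the unadjusted coefficient can reflect baseline severity plus regression to the mean rather than any association of behaviour with response. Under the assumed ranges with equal SDs it is about −0.08 to −0.24 for endpoints where higher is worse, with the sign reversed for FACIT-Fatigue, SF-12 and EQ-5D-3L. It needs a non-zero baseline correlation and depends on the SD ratio. The univariate logistic models with baseline behaviour have the matching problem in the opposite clinical direction.

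The documents do not support the stronger conclusion that the planned correlations are invalid or always biased. They give none of the correlations or SDs needed, and under a stable-level model the change score is the unbiased analysis. What the SAP lacks is a statement of what each coefficient estimates and an adjusted estimate to compare it with. The primary objective is not affected.

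**What to change.** Keep the planned coefficients and models. For the baseline-behaviour rows at M3, M6, M12 and M24, report beside them:

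- **Correlations:** the partial Pearson or Spearman correlation of behaviour with the visit value, given that endpoint's own baseline. For Pearson this is identical to the partial correlation with change, so one adjusted row per visit is enough.
- **Logistic models:** each model refitted with the baseline value of the index that defines the endpoint, namely DAS28-4 ESR, DAS28-4 CRP, SDAI, CDAI, the Boolean components or FiRST status. Baseline DAS28 should not stand in for all of them.

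State in SAP 8.1.2 and 8.1.3 that the unadjusted and adjusted estimates answer different questions, and that a change-score correlation will not be interpreted as a behavioural effect unless the two agree.

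The cost is a PARTIAL statement in PROC CORR, one covariate per logistic model (the components, for the Boolean definition) and a few lines of SAP text, using baseline data already scheduled. The downsides are more output, the loss of patients without a baseline value from the adjusted rows and models, and possible bias in the adjusted estimate if baseline is a noisy measure of a stable level.
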